Appendix 1: Pre-operative survey

Date ___/___/___ Surgeon _____ Participant ID _____

Pre-operative Survey

Welcome to Northwestern Prentice Women’s Hospital. Thank you for participating in a survey being conducted by [name] on the tolerance of chlorhexidine gluconate or povidone iodine vaginal cleansing solutions. Below are questions asking about any vaginal symptoms.

Please think back over the past 7 days...

1. VAGINAL DRYNESS				
What was the SEVERITY of your VAGINAL DRYNESS at its WORST?				
 None	 Mild	 Moderate	 Severe	 Very severe

2. VAGINAL BURNING				
What was the SEVERITY of your VAGINAL BURNING at its WORST?				
 None	 Mild	 Moderate	 Severe	 Very severe

3. VAGINAL ITCHINESS				
What was the SEVERITY of your VAGINAL ITCHINESS at its WORST?				
 None	 Mild	 Moderate	 Severe	 Very severe

4. UNUSUAL VAGINAL DISCHARGE				
Did you have any UNUSUAL VAGINAL DISCHARGE?				
 Not at all	 A little bit	 Somewhat	 Quite a bit	 Very much

5. PAIN OR BURNING WITH URINATION				
What was the SEVERITY of your PAIN OR BURNING WITH URINATION at its WORST?				
 None	 Mild	 Moderate	 Severe	 Very severe

6. OTHER SYMPTOMS				
Do you have any other symptoms that you wish to report?				
 Yes			 No	

Please list any other symptoms:	
1.	What was the severity of this symptom at its WORST?  None  Mild  Moderate  Severe  Very Severe

2.	What was the severity of this symptom at its WORST?  None  Mild  Moderate  Severe  Very Severe
----	------------------------------------------------------------------------------------------------------------------------------------------------------------------------------------------------------------

Appendix 2: Post-operative survey

Date ___/___/___ Surgeon _____ Participant ID _____

Post-operative Survey

Thank you for participating in a survey being conducted by [name] on the tolerance of chlorhexidine gluconate or povidone iodine vaginal cleansing solutions. Below are questions asking about any vaginal symptoms.

Please think back from immediately after your surgery to now....

1. VAGINAL DRYNESS				
What was the SEVERITY of your VAGINAL DRYNESS at its WORST?				
 None	 Mild	 Moderate	 Severe	 Very severe

2. VAGINAL BURNING				
What was the SEVERITY of your VAGINAL BURNING at its WORST?				
 None	 Mild	 Moderate	 Severe	 Very severe

3. VAGINAL ITCHINESS				
What was the SEVERITY of your VAGINAL ITCHINESS at its WORST?				
 None	 Mild	 Moderate	 Severe	 Very severe

4. UNUSUAL VAGINAL DISCHARGE				
Did you have any UNUSUAL VAGINAL DISCHARGE?				
 Not at all	 A little bit	 Somewhat	 Quite a bit	 Very much

5. PAIN OR BURNING WITH URINATION				
What was the SEVERITY of your PAIN OR BURNING WITH URINATION at its WORST?				
 None	 Mild	 Moderate	 Severe	 Very severe

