The study will take place at a single site, Northwestern Prentice Women's Hospital. Using a 2-sided test to detect a difference between proportions with 80% power and a 5% significance level, and assuming the prevalence of irritation in the control group (povidone iodine) is 10% and prevalence of irritation in the exposed group (chlorhexidine gluconate) is 31%, and factoring in patients lost to follow up given that the data collection is through a survey, the study will need 68 participants in each group. There are an estimated 800 hysteroscopies at Prentice Women's Hospital each year and given incomplete follow-up, we estimate it will take 6 to 8 months of patient enrollment to achieve this desired sample size.

STUDY-WIDE RECRUITMENT METHODS:

IRB #: STU00204759

The research coordinator will contact the appropriate gynecologic surgeons who will introduce the study to potential participants during the pre-operative office visit. On the day of surgery, prior to the administration of anesthetics, the patient will be asked of their willingness to participate in the study, and a study member will explain the risks and benefits. A written informed consent form will be filled out. Participants will be randomized through the use of Excel to generate randomization numbers to either experimental antiseptic, chlorhexidine gluconate, or the control, povidone iodine.

STUDY TIMELINES:

Participants will be involved in the study on the day of their surgery to 24-48 hours after surgery.

The proposed timeline of the study can be seen below:

- April- June 2017: Communicate with gynecologic surgeons operating at Prentice Women’s Hospital to gain awareness for the study. Communicate with preoperative nurses and operating room circulating nurses to make them aware of the logistics of study.
- July-February 2018: Recruit and enroll patients. Administer patient surveys.
- March- September 2018: Compile and analyze data

STUDY ENDPOINTS:

List of study variables to be collected:

Outcomes	Type	Definition
Vaginal dryness	Ordinal	Any sensation of dryness in the vagina
Vaginal burning	Ordinal	Any sensation of burning in the vagina
Vaginal itchiness	Ordinal	Any sensation of itchiness in the vagina
Unusual vaginal discharge	Ordinal	Any witness of unusual discharge coming from the vagina
Pain or burning with urination	Ordinal	Any sensation of pain or burning with urination

Exposures	Type	Definition

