Pre-op chlorhexidine gluconate	Dichotomous	If women randomized to receive chlorhexidine gluconate, then yes. If woman randomized to povidone iodine, then no.

Covariates	Type	Definition
-------------------	-------------	-------------------

Woman's Age	Continuous	Female age in years at time of surgery
Surgery	Nominal	Hysteroscopy, dilation and curettage, endometrial ablation or Essure.

Other	Type	Definition	Use
Gravidity	Count	Number of prior pregnancies	Table 1 population characteristic
Parity	Count	Number of pregnancies carried to a viable gestational age	Table 1 population characteristic
Race	Categorical	Group by race: White, Black/Africa-American, Hispanic, Asian/Pacific Islander, American Indian/Alaskan Native, Middle-Eastern	Table 1 population characteristic

PROCEDURES INVOLVED:

This is a single-blinded randomized control trial. The patients will be blinded to whether they receive the control povidone iodine or the experimental chlorhexidine gluconate antiseptic. The surgeons will be aware of the treatment, but will not be administering the survey questions to minimize bias.

Given the nature of the procedures included in the inclusion criteria, participants will present to the hospital on the day of their surgery and most will be discharged two to three to hours after surgery. Participants are expected to respond to the survey pre-operatively, prior to discharge from the hospital, and 24-48 hours after surgery. This corresponds to three total surveys per participant. The first two surveys done preoperatively and prior to discharge will be done on paper. A study member via phone will administer the third survey 24-48 hours after surgery. See Appendices 1 and 2 for sample pre-operative and post-operative surveys, respectively. The survey is six questions long, and should take no longer than 3-5 minutes to administer. The survey was designed using the PRO-CTCAE (Patient- Reported Outcomes version of the Common Terminology Criteria for Adverse Events) created by the NIH/NCI. The PRO-CTCAE is a measurement system used in cancer clinical trials to detect symptomatic adverse events. The language and format of the questions have been cognitively tested.¹¹ Questions 1,4,5, and 6 are part of the PRO-CTCAE question bank. Questions 2 and 3 on the survey were investigator-developed items to capture vaginal burning and itchiness, which are not contained in the PRO-CTCAE item library.

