The data to be collected will include: age, gender, race, gravidity, parity, surgeon, type of surgery, concomitant cystoscopy, use of Foley catheter, name of antiseptic solution, and presence and severity of vaginal and urinary symptoms based off survey responses. The patients will receive preoperative vaginal preparation either with povidone iodine or

chlorhexidine gluconate. Both antiseptic solutions are approved for surgical preparation of the vagina at Northwestern's Prentice Women's Hospital.

DATA & SPECIMEN MANAGEMENT:

Paper data will be stored in a locked cabinet at the nursing desk of the preoperative holding area and periodically transferred to a password protected Excel file on a password-protected laptop. Paper surveys will be stored for 1 years after the end date of the data collection (September 2019) and will be discarded through the hospital's confidential document shredding service. Electronic data will be de-identified and stored indefinitely on a password-protected computer.

The data will be transitioned to Excel and analyzed with a statistical software like SPSS. The participant's MRN will be collected in order to link survey data with patient demographics and the corresponding surgery/vaginal cleansing intervention. This MRN will be matched to a participant ID, and the survey will only have the patient's ID on it. The document linking MRN with participant ID will be kept separate from the surveys. The data collection spreadsheet will not contain patient MRNs.

PROVISIONS TO MONITOR DATA TO ENSURE THE SAFETY OF PARTICIPANTS:

The PI, [name], and researchers, [name], [name], [name], and one other research coordinator will have access to the data. The study team will evaluate the data collected every 2 weeks, and look at any adverse events to ensure patient safety. Safety information will be collected with case report forms. The Principal Investigator will be notified within 24 hours of learning of any serious adverse events, regardless of attribution, occurring during the study. The office of Risk Management and the IRB will be notified as soon as possible of "any unanticipated problems involving risk to subjects or others" (UPR/UPIRSO).

Contraindications:

Contraindications include patient with a history of the following after use of chlorhexidine gluconate or povidone iodine in any application:

- Atopic dermatitis
- Vaginal irritation
- Allergic reactions
- Anaphylaxis

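### Before discharge, question 5 cannot separate no pain on urination from not yet having urinated, and voiding status is not collected

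*Combined protocol and SAP*

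**What the plan says.** All references are to the combined protocol and SAP.

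- **Objectives.** Specific Aim 3 covers the presence and the severity of urinary pain or burning. It names no time point. The hypothesis is that vaginal and urinary symptoms will not differ significantly between the solutions.
- **Study Endpoints.** Urinary pain or burning is listed as an ordinal outcome, again with no time point and no rule for women who have not voided.
- **Procedures Involved, timing.** There are three surveys: before surgery, before discharge (both on paper) and by telephone at 24-48 hours. On discharge the section says that "most will be discharged two to three to hours after surgery".
- **Appendix 2.** One post-operative form is supplied. It asks the woman to look back over the time from the end of surgery to the moment she answers. Question 5 reads "What was the SEVERITY of your PAIN OR BURNING WITH URINATION at its WORST", with the answers None, Mild, Moderate, Severe and Very severe. There is no answer for not having urinated.
- **Procedures Involved, data to be collected.** The list includes "concomitant cystoscopy, use of Foley catheter". It does not include whether the woman has voided.
- **Study Analysis Plan.** The only test described is in the sample size statement: "Using a 2-sided test to detect a difference between proportions with 80% power and a 5% significance level". It assumes irritation rates of 10% and 31% and concludes that "the study will need 68 participants in each group".

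**The concern.** Question 5 presupposes an event, urination, that may not have happened when the pre-discharge form is filled in. The other four symptom items do not depend on an event in this way. For most women the look-back window at that survey is no more than about two to three hours.

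A woman who has not voided can tick None or skip the item. If she ticks None, her answer looks the same as that of a woman who voided without pain. If she skips it, the blank looks the same as any other missing answer. Because voiding is not recorded, neither can be sorted out afterwards. Foley use and cystoscopy are recorded, so those women can be identified, but that does not show who had voided.

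Equal numbers of such answers in the two arms do not cancel out of an absolute difference. They scale it down, and the hypothesis is one of no difference, so a smaller observed difference is easily read as confirming it. What is at stake is one of the two post-operative readings of an Aim 3 outcome.

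**Working it through.** **Inputs from the plan (Study Analysis Plan):** 10% (povidone iodine) and 31% (chlorhexidine) with irritation; two-sided 5% level; 80% power; 68 per group. Loss to follow-up is allowed for ("factoring in patients lost to follow up given that the data collection is through a survey"), but no percentage is given.

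**Inputs not in the plan (assumptions):** the urinary pain rates, for which the irritation rates are borrowed; and f, the share of women who have not voided when they fill in the pre-discharge form, varied from 10% to 30%.

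**Step 1. Reproduce the plan's figure.** Pooled formula without continuity correction, with a mean rate of (0.10 + 0.31)/2 = 0.205:

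n = [1.96 × √(2 × 0.205 × 0.795) + 0.84 × √(0.10 × 0.90 + 0.31 × 0.69)]² / 0.21² = 56.8, so 57 per arm.

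An assumed 15% loss gives 57/0.85 = 67.1, so 68. The stated 68 is therefore consistent with its inputs. It is sized on irritation, and nothing in this point alters it.

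**Step 2. Non-voiders tick None, same share f in both arms.** Observed rates are (1 − f) × 10% and (1 − f) × 31%, so the observed difference is (1 − f) × 21 points. The risk ratio stays at 31/10 = 3.10, because (1 − f) cancels.

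**Step 3. Non-voiders coded as not assessable.** The rates stay at 10% and 31% and the number per arm becomes 68 × (1 − f): 61, 54 and 48 for f = 10, 20 and 30%.

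Power is the exact binomial power of the pooled z test.

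| f | Rates if None | Difference if None | Power if None (68 per arm) | Difference if not assessable | Power if not assessable |
|---|---|---|---|---|---|
| 0% | 10.0% / 31.0% | 21.0 points | 88% | 21.0 points | 88% |
| 10% | 9.0% / 27.9% | 18.9 points | 83% | 21.0 points | 84% |
| 20% | 8.0% / 24.8% | 16.8 points | 77% | 21.0 points | 80% |
| 30% | 7.0% / 21.7% | 14.7 points | 71% | 21.0 points | 75% |

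Recoding gains only about 1, 2 and 4 points of power. Most of the fall from 88% comes from women who cannot yet answer, and no change to the form recovers that.

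**Step 4. Voiding differs by arm, non-voiders tick None.**

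- 80% of control and 60% of chlorhexidine women voided: 0.60 × 31% − 0.80 × 10% = 18.6% − 8.0% = 10.6 points; risk ratio 18.6/8.0 = 2.33.
- 60% and 80% voided: 0.80 × 31% − 0.60 × 10% = 24.8% − 6.0% = 18.8 points; risk ratio 24.8/6.0 = 4.13.

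So the risk ratio can move in either direction from 3.10, and the size of the distortion depends on facts the trial does not collect.

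**The case against.** **None may be a true answer.** The endpoint is any such sensation on urinating. A woman who has not urinated has felt none, so None can be read as correct for symptoms experienced by discharge. That is a legitimate quantity, but it differs from pain among women who have voided. The plan does not say which it means, and without voiding status a reader cannot tell how far the two diverge.

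**The next survey covers the gap.** The 24-48 hour call uses the same look-back from the end of surgery, so it takes in the pre-discharge interval and later voids. An analysis of that call, or of the worst post-operative answer, would be largely unaffected. This stands and limits the point. It does not remove it, because the plan names neither that survey nor any way of combining the two for Aim 3.

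**Restricting to voiders has its own risk.** Voiding happens after randomisation. If irritation leads women to delay it, a voiders-only comparison no longer has its randomised basis. This also stands, and it shapes the fix.

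**A stronger reading is not supported.** A reader might infer that women who have not voided are recorded as None and that the comparison is therefore diluted. The documents contain no such coding rule, and the pre-discharge form is on paper, so a blank is equally possible. Dilution follows only if these women tick None at similar rates in both arms, and then only for the absolute difference.

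**Conclusion.** The point holds as a modest defect of measurement. At the pre-discharge survey, question 5 cannot distinguish no pain from no urination, and the data collected do not allow this to be repaired later.

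Its size cannot be computed from the documents, which give neither urinary pain rates nor the share of women who have not voided. On the borrowed rates, and with equal shares ticking None, 10 to 30% not voided would cut a 21-point difference to between 18.9 and 14.7 points at that survey, with the risk ratio unchanged. With unequal voiding the bias could go either way. The benefit of recording voiding status is mainly interpretable data and an undistorted difference; the gain in power is small.

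A reader might go on to infer that Aim 3 as a whole is biased toward no difference. The documents do not support that: the 24-48 hour survey is largely unaffected, and no text makes the pre-discharge answer the Aim 3 result. It is a cheap improvement and no threat to the trial's main conclusion.

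**What to change.** 1. Add to question 5 of the pre-discharge form a tick-box such as: I have not urinated since surgery. Record it as its own category, never as None, and state how a blank is coded.
2. Name the 24-48 hour answer as the main Aim 3 result.
3. Report pre-discharge urinary pain as secondary. Show the number not voided by arm, and give results both for all women and for women who have voided, with a note that the latter comparison conditions on an event after randomisation.

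The cost is one tick-box, one coding rule and a sentence or two in the plan. There are three downsides. The item departs slightly from the layout of the library question. A sizeable share of answers at discharge may prove not assessable. The voiders-only result must be read with caution.
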